The occurrence of adverse events should be sought by non-directive questioning of the patient (subject) during the screening process after signing informed consent and at each visit during the study. Adverse events also may be detected when they are volunteered by the patient (subject) during the screening process or between visits, or through physical examination, laboratory test, or other assessments. As far as possible, each adverse event should be evaluated to determine:

1. The severity grade (CTCAE Grade 1-4)
2. Its duration (Start and end dates) or Ongoing at End of Study
3. Its relationship to the study treatment (Reasonable possibility that AE is related: No, Yes)
4. Action taken with respect to study or investigational treatment (none, dose adjusted, temporarily interrupted, permanently discontinued, unknown, not applicable)
5. Whether medication or therapy was given (no concomitant medication/non-drug therapy, concomitant medication/non-drug therapy)
6. Outcome (not recovered / not resolved, recovered / resolved, recovering / resolving, recovered / resolved with sequelae, fatal, unknown)
7. Whether it is serious, where a SAE is defined as in [Section 8.2.1](#).

All adverse events should be treated appropriately. If a concomitant medication or non-drug therapy is given, this action should be recorded on the Adverse Event eCRF.

Once an adverse event is detected, it should be followed until its resolution or until it is judged to be permanent, and assessment should be made at each visit (or more frequently, if necessary) of any changes in severity, the suspected relationship to the study treatment, the interventions required to treat it, and the outcome.

Progression of malignancy (including fatal outcomes), if documented by use of appropriate method (for example, as per RANO criteria for GBM), should not be reported as a serious adverse event.

Adverse events separate from the progression of malignancy (example, deep vein thrombosis at the time of progression or hemoptysis concurrent with finding of disease progression) will be reported as per usual guidelines used for such events with proper attribution regarding relatedness to the drug.

Whenever possible, a diagnosis should be reported instead of underlying signs and symptoms.

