14.3.1 Antitumor Effect – Definition

14.3.1.1 Evaluable for toxicity

All participants who receive at least one dose of study treatment will be evaluable for toxicity from the time of their first treatment.

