2.2 Analysis sets

Treatment group will be named as: Non Surg BGJ398 125 mg and Surg BGJ398 125 mg. If there are no patients in the surgery group, only Non Surg BGJ398 125 mg will be presented.

Full Analysis Set

The Full Analysis Set (FAS) includes all patients who received at least one dose of BGJ398. The FAS will be used for all listings of raw data. Unless otherwise specified the FAS will be the default analysis set used for all analyses.

Per protocol set (PPS)

The Per-Protocol Set (PPS) will consist of a subset of patients in the FAS (with FGFR1-TACC1, FGFR3-TACC3 and/or activating mutations in FGFR1, 2 or 3) who are compliant with requirements of the CSP. The PPS will include patients who have an adequate tumor assessment at baseline, a follow-up tumor assessment >8 weeks after starting treatment unless disease progression is observed before that time, and no protocol deviations.

[figure not shown]
Safety

The Safety Set includes all patients who received at least one dose of BGJ398 and have at least one valid post-baseline safety assessment.

The statement that a patient had no AE (on the AE (e)CRF) constitutes a valid safety assessment.

The treatment received is defined as:

- The treatment assigned if it was received at least once, or
- The first treatment received when starting therapy with study treatment if the assigned treatment was never received.

Patient Classification:

Patients may be excluded from the analysis populations defined above based on the protocol deviations entered in the database and/or on specific subject classification rules defined in Table 2-3.

Table 2-3 Determination of analysis set membership

Description used to report Protocol Deviations	Protocol deviation IDs	Analysis set(s) to be excluded
Inclusion criteria not met	INC01, INC02, INC04	PPS
Use of prohibited concomitant medication	WITH04, WITH05, TRT05	PPS

Withdrawal of Informed Consent

Any data collected in the clinical database after a subject withdraws informed consent from all further participation in the trial, will not be included in the analysis. The date on which a patient withdraws full consent is recorded in the (e)CRF.

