2.8 Safety analyses

A secondary objective of the study is to characterize the safety and tolerability of BGJ398.

The assessment of safety is based on the frequency and severity of AEs and SAEs, changes in hematology and chemistry values, specifically those associated with calcium/phosphate homeostasis and renal function, and on the number of laboratory values that fall outside of pre-determined ranges (CTCAE v 4.03 grading limits or normal ranges as appropriate). Other safety (e.g., ECGs, vital signs and special tests, e.g. pregnancy test) analyses will be considered as appropriate.

All safety analyses will be based on the safety set.

The safety summary tables will include only on-treatment assessments. All safety assessments will be listed, and those collected later than 30 days after study treatment discontinuation will be flagged.

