2.8.1 Adverse events (AEs)

AE summaries

AEs will be coded using MedDRA terminology, the latest version which will be available at the time of analysis.

AE summaries will include all AEs occurring during on treatment period. All AEs collected in the AE (e)CRF page will be listed along with the information collected on those AEs e.g. AE

relationship to study drug, AE outcome etc. AEs with start date outside of on-treatment period will be flagged in the listings.

AEs will be summarized by number and percentage of subjects having at least one AE, having at least one AE in each primary system organ class (SOC) and for each preferred term (PT) using MedDRA coding. A subject with multiple occurrences of an AE will be counted only once in the respective AE category. A subject with multiple CTCAE grades for the same preferred term will be summarized under the maximum CTCAE grade recorded for the event. AE with missing CTCAE grade will be included in the 'All grades' column of the summary tables.

In AE summaries, the primary system organ class will be presented alphabetically and the preferred terms will be sorted within primary SOC in descending frequency. The sort order for the preferred term will be based on their frequency.

The following adverse event summaries will be produced:

- Overview of adverse events and deaths (number and % of subjects who died, with any AE, any SAE, any dose reductions/interruptions, AE leading to discontinuation);
- AEs by SOC and PT, summarized by relationship (all AEs and AEs related to study treatment);
- Seriousness (SAEs and non-SAEs);
- Leading to treatment discontinuation;

The following listings will be produced:

- All adverse events (safety set)
- Adverse events among subjects who were not treated (all screened subjects)

Deaths

- Summaries for on-treatment and all deaths (including post-treatment death) will be produced by system organ class and preferred term.
- All deaths will be listed for the safety set, post treatment deaths will be flagged. A separate listing of deaths prior to starting treatment will be provided for all screened subjects.

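### The Safety Set requires a post-baseline safety assessment, so a dosed patient who dies very early with nothing else recorded would be missing from the death tables and listing

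*SAP*

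**What the plan says.** SAP 2.2 sets two conditions for safety analysis: "The Safety Set includes all patients who received at least one dose of BGJ398 and have at least one valid post-baseline safety assessment". Protocol 10.1.2 uses the same definition. Both documents then relax the second condition: "The statement that a patient had no AE (on the AE (e)CRF) constitutes a valid safety assessment" (SAP 2.2).

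Protocol Appendix 3, section 14.3.1.1, requires only the dose: "All participants who receive at least one dose of study treatment will be evaluable for toxicity from the time of their first treatment".

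The Safety Set governs every safety output. SAP 2.8 states: "All safety analyses will be based on the safety set". SAP 2.8.1 adds, for deaths: "All deaths will be listed for the safety set, post treatment deaths will be flagged". The only other death listing is for people who never started treatment: "A separate listing of deaths prior to starting treatment will be provided for all screened subjects". Likewise, the only AE listing in SAP 2.8.1 outside the Safety Set covers untreated screened subjects.

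Under protocol 8.1.1, deaths go on a Death form and CTCAE Grade 5 is not used. Documented progression, including a fatal outcome, "should not be reported as a serious adverse event".

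**The concern.** Whether a patient has a post-baseline assessment is known only after dosing, so the Safety Set is selected on something that happens after treatment starts. The dosed patients least likely to have one are those who die or leave within days of the first dose. A death in that window is the event a safety report most needs to show. If the death is recorded only on the Death form, the plan has no rule that brings the patient into the Safety Set, and both the death and the patient drop out of the death tables.

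The condition also gains nothing that either document states. The FAS already consists of everyone with at least one dose, so the extra condition can only remove patients. It conflicts with Appendix 3 for exactly those patients.

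**Working it through.** The plan gives no figure to reproduce. The check compares the definitions, follows one patient through the outputs, and then illustrates the size.

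**1. The two rules.** Protocol 10.1.2 and SAP 2.2 require a dose and a valid post-baseline assessment. Appendix 3, 14.3.1.1, requires a dose. They differ only for a dosed patient with no valid post-baseline assessment.

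**2. Where that patient would appear.**

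- Safety summaries (SAP 2.8): no, Safety Set only.
- Death summaries and death listing (SAP 2.8, 2.8.1): no, Safety Set only.
- Listing of deaths before treatment (SAP 2.8.1): no, the patient was treated.
- Exposure and dose summaries (SAP 2.4.1): no, Safety Set, although protocol 10.3.1 specifies the FAS.
- Disposition, end-of-treatment reasons and analysis-set counts (SAP 2.3.1): yes, FAS.
- Overall survival (OS) on the FAS (SAP 2.7.2): yes for Group 1; see step 4 for Group 2.

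SAP 2.2 also assigns all raw-data listings to the FAS, which does not fit with SAP 2.8.1 listing deaths on the Safety Set.

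**3. How a patient could lack a valid assessment.** The AE page would have to be blank, without even a statement of no AE, and there would have to be no post-dose test. From Cycle 1 this is hard to reach, because protocol 7.2.2.5.2 schedules phosphorus 8 hours after the first dose and again on Day 2. Group 2 before surgery is more exposed. Dosing runs 5 to 10 days. As far as Table 7-1 can be read, together with protocol 7.2.2.7.1, the scheduled tests are a pre-dose ECG on Day 1 and an ECG on the day of surgery. No laboratory, vital-sign or physical assessment is marked between them.

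**4. Group 2 and OS.** Protocol 10.5.2 counts OS from first treatment for Group 2 patients who do not have surgery, and excludes only those who have surgery and no post-surgical dose. SAP 2.7.2 omits the no-surgery clause and excludes any Surgery Group patient without a post-surgical dose. Read literally, a Group 2 patient who dies before surgery is outside the SAP's OS analysis as well as, in the case above, its death outputs.

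**5. Size (illustration).** Assume 34 dosed patients (protocol 10.4.1, SAP 1.1), k early deaths that fall outside the Safety Set, and d other on-treatment deaths. The documents give neither k nor d. All dosed: (d + k)/34. Safety Set as defined: d/(34 − k). Exact (Clopper-Pearson) 95% intervals are shown for d = 0.

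| k | d | All dosed | Safety Set as defined |
|---|---|---|---|
| 0 | any | d/34 | d/34, no change |
| 1 | 0 | 1/34 = 2.9% (0.1 to 15.3) | 0/33 = 0% (0 to 10.6) |
| 2 | 0 | 2/34 = 5.9% (0.7 to 19.7) | 0/32 = 0% (0 to 10.9) |
| 3 | 0 | 3/34 = 8.8% (1.9 to 23.7) | 0/31 = 0% (0 to 11.2) |
| 1 | 1 | 2/34 = 5.9% | 1/33 = 3.0% |
| 1 | 2 | 3/34 = 8.8% | 2/33 = 6.1% |

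**6. Opposite direction.** If the dropped patient leaves without an event, only the denominator shrinks. With three deaths among the others, 3/34 = 8.8% becomes 3/33 = 9.1%.

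**The case against.** The strongest reply is that almost nobody can fall into the gap. A patient with an AE has an AE record, and a patient without one qualifies through the statement of no AE. AEs are collected at every visit (protocol 7.2.2), and missing values are queried (protocol 9.4). Fatal events other than documented progression are SAEs, reportable regardless of causality (protocol 8.2). The progression rule removes SAE reporting only; it does not say the AE page stays blank. Table 7-1 is hard to read in the available text and shows no AE row, so an unmarked test there does not prove that no assessment takes place. Appendix 3 is a response-criteria appendix and does not define an analysis set.

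Most of this stands, and it limits the size of the problem. It does not close the gap, because a Death form still does not count and the death listing still excludes such a patient.

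A reader might also infer three stronger claims that the documents do not support:

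- **That all safety rates are biased downward.** The understatement applies to early deaths. Dropping an event-free leaver raises rates slightly (step 6).
- **That discontinuation rates are understated.** Discontinuations and their reasons are summarised on the FAS (SAP 2.3.1). The table of AEs leading to discontinuation uses the Safety Set, but a patient in it has an AE record.
- **That the patient vanishes from the report.** FAS disposition, the end-of-treatment listing and the analysis-set counts still show the patient, and OS on the FAS counts a Group 1 death.

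**Conclusion.** The point holds in a narrow form and is a minor improvement. The Safety Set in protocol 10.1.2 and SAP 2.2 conflicts with Appendix 3. As written, it would omit from the death summaries and listing a dosed patient who dies very early with a blank AE page and no post-dose test. A Group 2 patient who dies before surgery is the most exposed and, on a literal reading of SAP 2.7.2, would be missing from OS too.

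The number of such patients is unknown and may be zero, in which case nothing changes. With 34 dosed, one such patient lowers the reported death proportion by about 3 percentage points (2.9% to 0%, or 8.8% to 6.1% with two other deaths).

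The conclusion rests on two readings. One is that a valid assessment does not include a death, since neither document says that it does. The other is that an AE record or a post-dose test does count, although the documents name only the statement of no AE. The primary endpoint is not affected.

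**What to change.** In SAP 2.2, define the Safety Set as all patients who received at least one dose of BGJ398. Delete the post-baseline condition and the sentence on what counts as a valid assessment, which is then redundant. Record the departure from the protocol in SAP section 4, and align protocol 10.1.2 at the next amendment. The Safety Set then equals the FAS. This also removes the practical effect of the differences between protocol 10.3.1 and SAP 2.4.1 on exposure, and between SAP 2.2 and 2.8.1 on listings.

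If the two-condition definition is kept, the minimum is to state that a death counts as a valid safety assessment and to produce the death summaries and listing on the FAS.

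Neither option changes OS. The Group 2 wording in SAP 2.7.2 needs to be reconciled with protocol 10.5.2 separately.

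The cost is wording in the SAP and, because protocol 10.1.2 carries the same text, in a protocol amendment with the approvals that protocol 12.1 requires. No new data are needed.

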Evidence of FGFR1-TACC1, FGFR3-TACC3 fusion and/or activating mutation in FGFR1, FGFR2, or FGFR3 is required in order to begin study screening. [REDACTED]

- If pre-screening data is not available at the time of study entry, the patient must sign the molecular pre-screening consent to allow for the collection and/or submission of samples to the Novartis designated laboratory for analysis.

If the local data or the results of the central analysis meet inclusion criteria ([Section 5.2](#)), the patient can proceed with the screening procedures.

Patients identified to have an activating mutation in FGFR1, 2 or 3 may be eligible pending agreement between Novartis and Investigator.

Screening

The screening period begins once the patient has signed the study informed consent. All screening evaluations are required to be performed before study treatment administration begins. Evaluations that were conducted prior to the signing of the informed consent document as a part of standard of care analysis may be used to demonstrate eligibility as long as the evaluations were conducted within allowed screening windows.

Treatment period

For patients in group 1 (non surgical group, unresectable disease), the treatment period will begin on cycle 1, day 1 and will continue until disease progression, unacceptable toxicity, withdrawal of informed consent, or death.

For patients in group 2 (surgical group, resectable disease), the treatment will begin 5-10 days prior to surgery with the last pre-surgical dose given within 24 hours of surgery. The duration of the treatment before surgery (5 to 10 days) will be left at the investigator discretion. Patients will be expected to resume the treatment upon surgical recovery (a minimum of 2 weeks and no more than 6 weeks post operatively, unless agreed otherwise between Novartis and the Investigator, on a case by case basis). The post surgical treatment will begin as cycle 1, day 1 and will continue until disease progression, unacceptable toxicity, withdrawal of informed consent, or death.

End of treatment

The EOT visit occurs within 14 days after last administration of study treatment ([Section 7.1.4](#)). All participating patients must complete this visit even if they have had to discontinue prematurely unless they are unable or unwilling to return.

Follow up

All patients will be followed up as described in [Section 7.1.5](#).

30-day safety follow-up period

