6.3 Concomitant medications

The patient must notify the investigational site about any new medications he/she takes after the start of the study drug. All medications (other than study drug) and significant non-drug therapies (including physical therapy, herbal/natural medications and blood transfusions) administered during the study must be listed on the Concomitant Medications. If a drug is listed under "Permitted concomitant therapy requiring caution and/or action" and also under "Prohibited concomitant therapy", the drug should be prohibited.

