6.3.2 Permitted concomitant therapy requiring caution and/or action

Drugs that alter the pH of the GI tract

BGJ398 is characterized by pH-dependent solubility, and therefore, medicinal products that alter the pH of the upper gastro-intestinal tract may alter the solubility of both compounds, and limit bioavailability. These agents include, but are not limited to, proton-pump inhibitors (e.g., omeprazole), H₂-antagonists (e.g., ranitidine) and antacids. **Therefore, study drug(s) should be dosed at least 2 hours before or 10 hours after dosing with a gastric protection agent.** Note that some proton-pump inhibitors may inhibit BCRP.

Corticosteroids

Chronic dosing of corticosteroids such as dexamethasone and prednisone is known to induce CYP3A enzymes, thereby increasing the risk of reducing drug exposure to sub-therapeutic levels. In addition BGJ398 is an *in vitro* inhibitor of CYP3A4 and has the potential to increase the systemic exposure of corticosteroids that are metabolized by CYP3A4.

Systemic corticosteroid treatment can be used with caution and minimized to the extent possible.

Substrates and inhibitors

CYP substrates and inhibitors

BGJ398 was shown to inhibit the cytochrome p450 isoenzyme CYP3A4 in *in-vitro* assays, thus, suggesting an increased risk of drug interactions with concomitant medications that are metabolized by CYP3A4. However, such interactions have not been confirmed in patients. Therefore, investigators may administer medications that are known to be metabolized by CYP3A4. Patients must be monitored for potentiation of toxicity and may require dose titration or reduction of the CYP3A4 substrate. In particular caution is advised when substrates with a narrow therapeutic index, such as alfentanil, fentanyl, astemizole, cisapride, diergotamine, ergotamine, pimozone, quinidine, sirolimus, tacrolimus, and terfenadine need to be administered. Please refer to [Appendix 1](#) for the list of medication to be used with caution.

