14.2 Appendix 2: List of prohibited medication

Table 14-2 List of prohibited medication while on the study

Category	Drug Names
Strong inducers of CYP3A4	Avasimibe, carbamazepine, phenobarbital, phenytoin, rifabutin, rifampin, St. John's wort
Strong Inhibitors of CYP3A4	Clarithromycin, conivaptan, indinavir, itraconazole, ketoconazole, voriconazole, lopinavir, mibefradil, nefazodone, nelfinavir, posaconazole, ritonavir, saquinavir, telithromycin, grapefruit juice, juice from Seville oranges, star fruits, pomegranates and pummelos.
Medications which increase serum phosphorus and/or calcium	Calcium, phosphate, vitamin D, parathyroid hormone (PTH)
Narrow Therapeutic index substrates of CYP3A4	Quinidine, astemizole, terfenadine, cyclosporine, sirolimus, tacrolimus, diergotamine, cisapride, ergotamine, pimozide, alfentanil, fentanyl thioridazine, diergotamine, dihydroergotamine, ergotamine
Medications with established potential for QT prolongation or Torsades de pointes	Amiodarone, Anagrelide, Arsenic trioxide, Astemizole (Off US mkt), Azithromycin, Bepriidil (Off US mkt), Chloroquine, Chlorpromazine, Cisapride (Off US mkt), Citalopram, Clarithromycin, Cocaine, Disopyramide, Dofetilide, Domperidone (Not on US mkt), Dronedarone, Droperidol, Erythromycin, Escitalopram, Flecainide, Grepafloxacin (Off market worldwide), Halofantrine, Haloperidol, Ibutilide, Levofloxacin, Levomethadyl (Off US mkt), Mesoridazine (Off US mkt), Methadone, Moxifloxacin, Ondansetron, Pentamidine, Pimozide, ProbucoI (Off US mkt), Procainamide (Oral off US mkt), Quinidine, Sevoflurane, Sotalol, Sparfloxacin (Off US mkt), Sulpiride (Not on US Mkt), Terfenadine (Off US mkt), Thioridazine, Vandetanib

Table 14-3 EIAEDs that are prohibited

Strong CYP3A inducers	Moderate CYP3A inducers
carbamazepine	felbamate
phenobarbital	topiramate (>200 mg/day)
phenytoin	oxcarbazepin
fosphenytoin	eslicarbazepin
primidone	rufinamide

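### The SAP's PPS rules can remove operated Group 2 patients from the primary analysis set because of drugs given for their planned surgery

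*SAP*

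**What the plan says.** **Primary set.** Protocol 10.4.1 and SAP 2.5.2 place the primary analysis on the PPS. The protocol gives 24 patients, with both groups pooled.

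**Exclusion.** SAP 2.2 says: "Patients may be excluded from the analysis populations defined above based on the protocol deviations entered in the database". Table 2-3 then maps "Use of prohibited concomitant medication" (IDs WITH04, WITH05 and TRT05) to exclusion from the PPS. The SAP's PPS definition ends "unless disease progression is observed before that time, and no protocol deviations"; Protocol 10.1.3 requires only that there be no major deviation.

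**Prohibited drugs.** Protocol Table 14-2 applies while a patient is on the study. Its narrow-therapeutic-index row includes "ergotamine, pimozide, alfentanil, fentanyl thioridazine". Its QT row includes "Quinidine, Sevoflurane, Sotalol", and also droperidol, haloperidol and ondansetron. Section 6.3.3 adopts the QT list and makes no exception for surgery.

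**Other text on the same drugs.** Section 6.3.2 says: "In particular caution is advised when substrates with a narrow therapeutic index, such as alfentanil, fentanyl". It also asks that alfentanil be avoided where possible, and it allows anti-emetics with a known torsades risk under caution. Table 14-1 lists ondansetron for caution only. For a drug under both the caution and the prohibited heading, section 6.3 says "the drug should be prohibited".

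**Surgery.** Group 2 takes BGJ398 for 5 to 10 days before a planned resection, "with the last pre-surgical dose given within 24 hours of surgery". Treatment resumes 2 to 6 weeks later as Cycle 1 Day 1. PFS for operated patients runs from that first post-surgical dose (Protocol 10.4.1, SAP 2.5.1).

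**The concern.** Group 2 is defined by an operation that takes place after study drug has started. Some drugs that may be given at that operation are on the prohibited list, and the SAP links prohibited use to loss of PPS membership. Followed as written, the rule can drop a patient because of the operation that put the patient in Group 2, and before that patient's endpoint begins.

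The exposure depends on group. A Group 1 patient may have been resected up to six weeks before the first dose (inclusion criterion 7). That patient's anaesthetic precedes study treatment, so it is not on-study use (exclusion criterion 12 bars QT-prolonging drugs only in the last 7 days before dosing). A Group 2 patient given the same agent a few days after starting BGJ398 can be removed. The plan pools the groups because it expects similar PFS6 in both; a filter that acts mainly on one of them undermines that pooling.

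**Working it through.** **Step 1. Follow one operated patient through the text.**

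| Step | Source | Result |
|---|---|---|
| BGJ398 on the day of surgery or the day before | Protocol 4.1, 7.1.3 | Patient is on study |
| Sevoflurane given | Table 14-2 QT row, adopted by 6.3.3 | Prohibited, no exemption |
| All medications given during the study must be listed | Protocol 6.3 | Use is recorded |
| No authorised deviations | Protocol 12 | No waiver route |
| Table 2-3 row, or the no-deviation definition | SAP 2.2 | Patient can leave the PPS |
| First post-surgical dose, at least 2 weeks later | Protocol 10.4.1 | PFS clock starts only now |

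Haloperidol follows the same path. Ondansetron is on both lists, and the tie-break in 6.3 makes it prohibited. Droperidol is in the QT row, although 6.3.2 allows some anti-emetics with caution. Fentanyl and alfentanil are less clear. The tie-break refers to the headings of 6.3.2 and 6.3.3, and 6.3.3 does not name narrow-therapeutic-index CYP3A4 substrates; only Table 14-2 does.

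**Step 2. How many.** Protocol 4.1 expects about 2:1 for Group 1 to Group 2. Assuming that ratio holds in the PPS, Group 2 is 24/3 = 8. Section 7.1.4.2 allows no replacement. Losing half leaves 24 − 4 = 20; losing all leaves 24 − 8 = 16. The documents do not say how often these drugs would be used.

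**Step 3. Reproduce the plan's figure.** Model from Protocol 10.4.2: Weibull with log λ ~ N(0, 2.236), ν ~ Exp(1), time in months, PFS6 = exp(−λ·6^ν). Each posterior was computed on a grid. Accrual is one patient per month. The interim is at 10 patients and the final at 24, each 6 cycles after the last patient needed: 6 × 28 / 30.4375 = 5.52 months. Assumption: true PFS is exponential with S(6) = p, so at p = 0.50 the rate is −ln(0.50)/6 = 0.1155 per month.

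- Prior check: P(PFS6 < 16%) = 0.647 and P(PFS6 > 40%) = 0.260; the plan states 65% and 25%.
- Success with 24 patients, 4,000 trials: 0.861 at p = 0.50 (plan 0.861), 0.461 at 0.40 (plan 0.465), 0.019 at 0.25 (plan 0.026).
- Stopping at interim at p = 0.50: 0.041 (plan 0.039).
- Mean events at p = 0.50 were 19.5 against the plan's approximate 17, so follow-up is not matched exactly.

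**Step 4. Shrink the PPS.** Probability of success, 4,000 trials per cell:

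| PPS size | p = 0.50, with interim | p = 0.50, no interim | p = 0.25, with interim |
|---|---|---|---|
| 24 | 0.861 | 0.876 | 0.019 |
| 20 | 0.844 | 0.860 | 0.030 |
| 16 | 0.807 | 0.812 | 0.045 |

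The no-interim column matters because SAP section 4 says that no interim was performed. Simulation error near 0.86 is √(0.861 × 0.139 / 4000) = 0.005. The drop of 0.861 − 0.844 = 0.017 is therefore small against the noise, and the drop of 0.861 − 0.807 = 0.054 is clear. Censoring every patient at 6 months (1,500 trials each, with interim) gives 0.829, 0.827 and 0.777: almost no effect at 20 and about 5 points at 16.

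**The case against.** The strongest reply is that the exclusion is not shown to operate. Table 2-3 works through three coded IDs that the documents do not define, SAP 2.2 says patients may be excluded, and deviation categories sit in a Data Handling Plan that is not available here. The row could be narrower than its label. This stands: a reader might infer that every operated patient given a listed drug leaves the PPS automatically, and the text does not support that. It does not dispose of the point, because the SAP's separate no-deviation wording leads to the same exclusion once the use is recorded as a deviation.

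A reader might also take fentanyl and alfentanil as plainly prohibited. The documents contradict themselves on these two, so the argument rests on sevoflurane, haloperidol, droperidol and ondansetron.

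It can also be said that the loss is only one of precision. The plan expects equal PFS6 in the two groups, and on that premise dropping Group 2 does not shift the estimate. That is fair, and the loss of power is modest.

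Finally, Protocol 10.4.4 repeats the primary model on the FAS, and SAP 2.3.1 tabulates deviations that lead to exclusion. This helps only in part. The FAS includes the amplification patients whom the protocol keeps out of its efficacy focus, and SAP 2.5.4 specifies Kaplan-Meier estimates without repeating the Bayesian model on the FAS.

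**Conclusion.** The point holds as a conditional one. If medication for the planned surgery is coded under WITH04, WITH05 or TRT05, or is recorded as any deviation, operated Group 2 patients can be dropped from the primary set for an exposure before their PFS clock starts. The surgery is routine care, but it defines Group 2 and is on the visit schedule.

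The number affected is unknown. SAP 2.2 allows for an empty surgery group, and then there is no effect. If Group 2 were 8 of 24, the probability of success at a true PFS6 of 50% would fall by about 2 points (half lost) or 5 points (all lost). At a true PFS6 of 25% it would rise from 0.019 to 0.030 or 0.045. These figures assume the 2:1 ratio in the PPS, no replacement and exponential PFS. The more important consequence is the selective loss of one of two pooled groups.

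A reader might infer that the row favours the drug, for instance by removing patients who need an enzyme-inducing anti-epileptic as the tumour worsens. The documents do not establish that. Protocol 6.3.3 takes such patients off study unless they are felt to have benefited, and the RANO appendix separates seizures from tumour-related deterioration. The direction of any bias is open.

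**What to change.** In SAP 2.2, before database lock:

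1. Return the PPS definition to the protocol's limit, no major deviations, and list which deviations count as major, as Protocol 10.1.3 promises.
2. Define WITH04, WITH05 and TRT05.
3. State in Table 2-3 that medication given for the planned Group 2 surgery before Cycle 1 Day 1 does not by itself exclude a patient from the PPS.

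Item 3 alone is not enough, because the no-deviation wording would still exclude these patients. Leave the handling of later prohibited anticancer therapy unchanged. A broader rule that kept all later prohibited-drug users would also keep patients given another anticancer agent, and SAP 2.5.3 has no censoring rule for new therapy.

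Separately, Protocol 6.3, 6.3.2, 6.3.3, Table 14-1 and Table 14-2 must be reconciled with each other and with the Group 2 surgical phase. No position is taken here on which drugs should be allowed.

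The cost is wording in one SAP section and a protocol clarification. No new data are needed.
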